**01-03-2018**

**Unique Protocol ID: IRB 2017-215**

**NCT03404700**

## **Summary**

Eggs are nutrient dense, convenient, affordable, and provide key macro and micronutrients in one's diet. Despite having a lot of benefits of consuming eggs in relation to health recent epidemiological studies raise health concerns about egg intake for subgroups of people. For instance, under free-living conditions, higher egg intake is associated with increased cardiovascular disease (CVD) risk in diabetic individuals as well as increased risk of developing type 2 diabetes. However, these studies do not establish that egg consumption "causes" health issues.

It is also possible that the association of egg intake with increased CVD risk in diabetics, or with a greater risk of developing diabetes, is simply due to the other foods that people usually eat with eggs, such as saturated fats, and not due to eggs *per se*.

For part I, the investigators propose to test this hypothesis by determining the food intake of 48 non-diabetic individuals under free-living conditions using the remote food photography method (RFPM), which uses smartphone technology. The frequency of egg consumption will be obtained using a food frequency questionnaire (FFQ). In addition, participants will record their food intake using food record diary and a 24-hour food recall method. Energy intake information gathered from RFPM will be compared with the 7-day food record and the 24-hour recall.

Next, for part II, the same study participants will be offered four separate test breakfasts of similar calories, containing 1) Eggs; 2) Eggs with a high amount of saturated fat; 3) Cereal breakfast (neither eggs nor saturated fat); or 4) Cereal breakfast with a high amount of saturated fat. Alteration of blood glucose, insulin, hunger, and satiety hormones (ghrelin, PYY, GLP-1), and metabolic rate will be measured before and after each breakfast in part II.

The investigators expect to determine if the purported association of eggs to alterations in glucose control and related metabolic alterations are independent of eggs, but mainly due to saturated fat is eaten along with eggs rather than the egg consumption itself.

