## **B. Hypotheses:**

These aims will test the following hypotheses:

1. Meals that include eggs will have higher energy and saturated fat contents as determined by RFPM, compared to corresponding meals (i.e. breakfast, lunch, or dinner) without eggs.
2. As determined by RFPM, individuals of the study sample who will be in the highest quartile in terms of egg consumption in the free-living condition (defined as high egg consumers) will have a higher intake of saturated fat and total energy as compared to individuals who will be in the lowest quartile in terms of egg consumption (defined as low egg consumers).
3. Baseline insulin level, blood glucose level, the Homeostatic Model Assessment (HOMA) index of insulin resistance using fasting glucose and insulin levels, and HbA1C will be positively associated with total EI and saturated fat intake determined by RFPM, even when adjusted for age, sex, BMI and waist circumference
4. Above outcome variables will not be associated with egg intake determined by RFPM.

5. In the randomized partial crossover study, presence of eggs in the breakfast will be associated with a) a greater increase (i.e. both area under the curve and pre-post change) in satiety hormones (i.e. PYY and GLP-1), b) a less profound increase in blood glucose and insulin levels, c) a greater decrease in the hunger hormone (ghrelin) and d) an increase in the area under the curve of metabolic rate when controlled for the content of saturated fat in the test diets.
6. In the randomized partial crossover study, presence of a high amount of saturated fat in the breakfast will be associated with a) a greater increase (i.e. both area under the curve and pre-post change) in satiety hormones (i.e. PYY and GLP-1), b) a less profound increase in blood glucose and insulin levels, c) a greater decrease in the hunger hormone (ghrelin) and d) an increase in the area under the curve of metabolic rate when controlled for the presence of eggs in the test diets.
7. In the randomized partial crossover study, the associations mentioned in hypothesis 5 will be moderated by the presence of a high amount of saturated fat in the diet.
8. Estimates of total EI by RFPM will be significantly greater than EI estimates by 7-day food record and the 24-hour recall in dietary assessment.

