### **Outcome Measures:**

#### **A. Primary Outcome Measures:**

1. Difference of energy intake (kcal) in meals containing eggs as compared to meals that do not contain eggs

Energy intake will be determined using Remote Food Photography Method (RFPM) and the meals of all test subjects will be categorized based on the presence or the absence of eggs in the meals.

[Time Frame: Day 1-7 of the ecological momentary assessment part (Part I) of the study]

2. Difference of energy intake (kcal) in high egg consumers as compared to low egg consumers  
Comparison of mean daily energy intake as measured by Remote Food Photography Method (RFPM) between high egg consumers and low egg consumers identified by providing a food frequency questionnaire (FFQ).

[Time Frame: Day 1-7 of the ecological momentary assessment part (Part I) of the study]

3. Difference of saturated fat (g) intake in meals containing eggs as compared to meals that do not contain eggs

Saturated fat intake will be determined using Remote Food Photography Method (RFPM) and the meals of all test subjects will be categorized based on the presence or the absence of eggs in the meals.

[Time Frame: Day 1-7 of the ecological momentary assessment part (Part I) of the study]

4. Difference of saturated fat (g) intake in high egg consumers as compared to low egg consumers

Comparison of saturated fat intake as measured by Remote Food Photography Method (RFPM) between high egg consumers and low egg consumers identified by providing a food frequency questionnaire (FFQ).

[Time Frame: Day 1-7 of the ecological momentary assessment part (Part I) of the study]

5. Difference of blood glucose levels compared between different test breakfasts

This will be measured on visit 1 and 2 after providing test breakfasts.

[Time Frame: Changes in concentration (area under the curve; AUC) from 30 minutes prior to breakfast to 180 minutes after consumption of test breakfasts (Part II of the study)]

6. Difference of insulin levels compared between different test breakfasts

This will be measured on visit 1 and 2 after providing test breakfasts.

[Time Frame: Changes in concentration (area under the curve; AUC) from 30 minutes prior to breakfast to 180 minutes after consumption of test breakfasts (Part II of the study)]

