**Statistical Analyses Plan (SAP):**

Data will be imported to R statistical software and the distributions will be examined visually to make a decision about the appropriate statistical tests (i.e. parametric / non-parametric) to be used for all comparisons. All statistical analyses will be conducted using R statistical software. Family-wise error rate will be maintained at 0.05.

Free living EI and saturated fat intake during main three meals (i.e. breakfast, lunch and dinner) of each subject will be determined using RFPM and the meals of all test subjects will be categorized based on the presence or the absence of eggs in the meals. Means of EI and saturated fat intake during each main meal will be compared between the two categories (i.e. eggs present vs. eggs absent) using multi-level mixed-effects regression models constructed using the lmerTest package in R statistical software. Age, sex, baseline BMI and / or waist circumference will be included in the models as subject-level covariates.

Based on RFPM data, mean EI and saturated fat intake of the high egg consumers (i.e. individuals in the top quartile based on egg consumption) will be compared with the mean EI and saturated fat intake of the low egg consumers (i.e. individuals in the bottom quartile based on egg consumption) via Welch t-tests or the Wilcoxon test, depending on the distributions of the data.

Linear regression models will be constructed to examined the associations between a) total EI, b) saturated fat intake and c) egg intake and each of i) baseline insulin level, ii) blood glucose level, iii) HOMA-IR, and iv) HbA1C level. The usual regression assumptions will be assessed and any concerns will be ameliorated as appropriate (e.g. apply a transformation as guided by Box-Cox)

Using the data obtained in the randomized partial crossover trial, multi-level mixed effects regression models will be constructed using the lmerTest package in R statistical software to predict each of a) PYY (AUC and pre-post change); b) GLP-1 (AUC and pre-post change); c) ghrelin (AUC and pre-post change); d) blood glucose (AUC and pre-post change); e) insulin (AUC and pre-post change); f) metabolic rate using i) the presence of eggs in the diet; ii) the

presence of a high content of saturated fat in the diet; iii) their interaction. Age, sex, baseline BMI and / or waist circumference will be included in the models as subject-level covariates.

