Mean EI estimates of food records and 24-hour recall methods will be compared with the EI estimates of RFPM both with and without controlling for age, sex, baseline BMI and / or waist circumference by constructing a mixed-effects regression model to predict EI using the lmerTest package in R statistical software. The methods of estimation will be included in the model as a categorical independent variable and RFPM will be specified as the reference category. Age, sex, baseline BMI and / or waist circumference will be included in the models as subject-level covariates.

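### Primary outcomes 1 and 3 compare whole meals with the egg included, so a positive result cannot by itself show that the foods eaten with eggs carry the excess

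*Combined protocol and SAP*

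**What the plan says.** The Summary proposes that the reported association "is simply due to the other foods that people usually eat with eggs, such as saturated fats, and not due to eggs" themselves, and continues: "For part I, the investigators propose to test this hypothesis by determining the food intake of 48 non-diabetic individuals".

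Hypothesis 1 concerns whole meals: "Meals that include eggs will have higher energy and saturated fat contents as determined by RFPM". Primary outcome 3 is the "Difference of saturated fat (g) intake in meals containing eggs as compared to meals that do not contain eggs", and outcome 1 is its energy counterpart. Outcomes 2 and 4 compare consumer groups, for example "Difference of saturated fat (g) intake in high egg consumers as compared to low egg consumers".

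For outcomes 1 and 3 the SAP says "Means of EI and saturated fat intake during each main meal will be compared between the two categories", egg present and egg absent. It uses multi-level mixed models with subject-level covariates (age, sex, BMI and/or waist). It states neither the random effects nor a within-subject term.

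Four other places bear on the point:
- Hypothesis 4 is worded "Above outcome variables will not be associated with egg intake determined by RFPM", so egg amounts have to be obtained from the images. The RFPM section promises only energy and macronutrients back from the image analysis.
- Appendix F asks about cooking fat, bacon and hash browns eaten with eggs. No analysis of these items is planned.
- The Significance section leaves the link between the accompanying dietary pattern and adverse outcomes to future research.
- The attached 40-subject proposal mentions, in its Research plan overview, comparing the saturated fat that accompanies eggs between low and high consumers. It also lists a within-subject meal comparison. Neither is spelled out in the current SAP.

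**The concern.** A whole-meal total is the egg plus everything else on the plate. If egg meals turn out richer, the cause may be the egg, the bacon and butter beside it, or both, and the planned contrast returns only the sum. The Summary's hypothesis is about the second source.

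The over-reading is foreseeable: the attached proposal expects egg meals to be richer because of the foods that accompany them. Reported alone, a positive outcome 1 or 3 could be presented as evidence for the Part I hypothesis when it shows only that egg meals contain more.

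A smaller, related point concerns the model. If it has a single egg-present term, the coefficient can absorb some difference between people who often eat eggs and people who seldom do.

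**Working it through.** **1. The plan's own figures.** The attached proposal claims 80% power with 40 subjects for an effect size of 0.45 or a correlation of 0.43. A two-sided paired t-test at 0.05 gives 0.454, and Fisher's z gives 0.431. Both reproduce; the point does not depend on them.

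**2. What each contrast estimates.** Let e be the egg's content, r the content of any item it replaces (r ≥ 0), and d the difference in the remaining foods.
- Whole-meal contrast: d − r + e.
- Egg-excluded contrast: d − r.

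With d = 0 and r = 0 the whole-meal contrast equals e, which is positive with identical accompanying foods. If r = e and d = 0 it is zero. If d − r > 0, then d > 0 and the whole-meal contrast is positive too.

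**3. What the documents say about e.** Table 1 gives breakfast A, with two eggs, 5.193 g saturated fat in total, so two eggs contribute at most 5.193 g. The egg-minus-cereal differences are 5.193 − 2.916 = 2.277 g (A − C) and 10.893 − 10.616 = 0.277 g (B − D). Milk, bread and spreads also differ, so neither isolates the egg. No meal SD is given, so the rest is in meal-SD units.

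**4. Precision.** Assumptions: 48 subjects (Overview), 7 meals of one type each (7 days), and subject egg propensity logit-normal with SD 1. The within-subject contrast has SE ≈ 1/√(48 × 6 × E[p(1−p)]).

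| Mean egg-meal share (assumed) | E[p(1−p)] | SE (meal SD) |
|---|---|---|
| 42% | 0.202 | 1/√58.1 = 0.131 |
| 22% | 0.148 | 1/√42.7 = 0.153 |
| 8% | 0.069 | 1/√20.0 = 0.224 |

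**5. Chance that the egg alone gives a significant positive contrast (d = r = 0).** This is 1 − Φ(1.96 − e/SE), two-sided 0.05.

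| e (meal SD) | 42% share | 22% share | 8% share |
|---|---|---|---|
| 0.2 | 1 − Φ(1.96 − 1.52) = 33% | 1 − Φ(1.96 − 1.31) = 26% | 1 − Φ(1.96 − 0.89) = 14% |
| 0.5 | 1 − Φ(1.96 − 3.81) = 97% | 1 − Φ(1.96 − 3.27) = 90% | 1 − Φ(1.96 − 2.23) = 61% |

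Simulating a random-intercept model with a single egg-present term (between-person SD 1/3 or 1 meal SD, three covariates) gives 28–39% and 90–99% at shares of 22–42%. Together the two methods span 26–39% and 90–99%. At 0.05/6 (an assumed Bonferroni split over the six primary outcomes) the formula gives 9–13% and 74–88%.

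**6. The egg-excluded contrast in the same setting (22–42% shares).** By simulation its 95% interval lies wholly above zero in 2.4–2.8% of studies if eggs replace nothing, and in under 0.1% if they replace an item worth 0.2 meal SD. For 80% power it needs d − r of 2.80 × SE: 2.80 × 0.131 = 0.37 to 2.80 × 0.153 = 0.43 meal SD. At an 8% share this is 2.80 × 0.224 = 0.63.

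**7. Mixing of within- and between-person differences.** Simulated with no within-person effect, between-person SD 1–3 g and meal SD 3–6 g (all assumed), single-term false positives are 5–8% when egg propensity and usual intake correlate 0.3, and 10–19% at 0.7. With each subject's egg-meal share in the model they are 4–6%, and the SE is 2–15% larger.

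**The case against.** A reader might infer that outcomes 1 and 3 are invalid, or that Part I has no route to its hypothesis. The documents support neither. Hypothesis 1 is about whole meals, and whole-meal totals test it. The regressions for Hypotheses 3 and 4 relate glycaemic markers to energy, saturated fat and egg intake, and Part II varies eggs and saturated fat factorially. These address the wider hypothesis. They do not show what accompanies eggs in free-living meals, so the gap is confined to the intake contrasts in outcomes 1 to 4.

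The plan is also not silent on interpretation. The Significance section defers the question of eggs themselves against the accompanying pattern, as a cause of adverse outcomes, to future research. That is a real limit on the outcome claim, but it is not a rule for reading a positive Hypothesis 1. The attached proposal's phrase about fat accompanying eggs shows the idea was considered; it concerns low against high consumers, is not defined as egg-excluded, and is in neither analysis list.

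Three criticisms of the size and remedy stand. The rates follow from the assumed egg contribution and egg-meal share, and are lower where eggs are rare, as they may be at lunch or dinner. The egg-excluded contrast is biased downward when eggs replace something: if nothing else differs and the replaced item is worth 0.2 or 0.3 meal SD, its interval lies wholly below zero in about 25–34% or 50–63% of studies. The food record is a weak substitute, because Hypothesis 8 expects it to give lower energy than RFPM.

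**Conclusion.** The point holds as a limit on inference; it does not fault the primary test. A positive outcome 1 or 3 shows that egg meals are richer. It cannot alone show that the accompanying foods make them so.

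How often the egg alone would produce such a result cannot be fixed from the documents. Under the assumptions in steps 4 and 5 it ranges from about one study in seven (0.2 meal SD, 8% share) to nearly all (0.5 meal SD, 42% share). It would be wrong to infer that a positive contrast must be due to the egg: substitution can shrink or remove the whole-meal excess.

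The mixing problem is secondary. It is small unless egg habit and usual intake are strongly correlated, and the planned covariates may absorb part of it. The change is worth making because it is cheap and bears directly on the question the Summary sets for Part I. Confidence is medium.

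**What to change.** Keep the whole-meal contrast as the primary test of Hypothesis 1, and add three things to the SAP.

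1. **Model.** Fit a random intercept for subject and include each subject's proportion of egg-containing meals of that meal type, so that the egg-present coefficient is the within-subject contrast.
2. **Supportive, non-primary analysis.** If RFPM item-level or per-meal egg output can be obtained, analyse energy and saturated fat from the non-egg items with the same model. Subtract the egg ingredient of mixed dishes and count added cooking fat as non-egg. Report the estimate with its 95% confidence interval beside the whole-meal estimate, and note that it is biased downward when eggs replace another item. An interval wholly above zero supports accompanying foods; anything else is reported as not demonstrating it.
3. **Interpretation.** State that a positive whole-meal contrast alone will not be reported as showing that accompanying foods carry the excess.

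The 7-day food record may serve only as an exploratory fallback, labelled as self-report. Its energy is already to be estimated ("Mean EI estimates of food records and 24-hour recall methods will be compared with the EI estimates of RFPM"), but its saturated fat would need extra coding. If no item-level data exist, adopt items 1 and 3.

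**Cost.** One model term, one derived variable per meal, and a data request best made before the images are coded. The SE is about 2–15% wider. The supportive contrast is conservative and has limited power, as step 6 shows, most of all at meals where eggs are rare.

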## **B. Secondary Outcome Measures:**

1. Difference of subjective hunger level compared between different test breakfasts

This will be measured on visit 1 and 2 after providing test breakfasts.

[Time Frame: Changes in scores (arbitrary units AU) from 30 minutes prior to breakfast to 180 minutes after consumption of test breakfasts (Part II of the study)]

2. Difference of subjective satiety level compared between different test breakfasts

This will be measured on visit 1 and 2 after providing test breakfasts.

[Time Frame: Changes in scores (arbitrary units AU) from 30 minutes prior to breakfast to 180 minutes after consumption of test breakfasts (Part II of the study)]

3. Difference of objective hunger compared between different test breakfasts

This will be measured on visit 1 and 2 after providing test breakfasts by measuring serum ghrelin levels.

[Time Frame: Changes in concentration (area under the curve AUC) from 30 minutes prior to breakfast to 180 minutes after consumption of test breakfasts (Part II of the study)]

4. Difference of objective satiety compared between different test breakfasts using serum Glucagon-like peptide-1 (GLP-1) levels.

This will be measured on visit 1 and 2 after providing test breakfasts by measuring serum GLP-1 levels.

[Time Frame: Changes in concentration (area under the curve AUC) from 30 minutes prior to breakfast to 180 minutes after consumption of test breakfasts (Part II of the study)]

5. Difference of objective satiety compared between different test breakfasts using serum Peptide YY (PYY 3-36) levels

This will be measured on visit 1 and 2 after providing test breakfasts by measuring serum PYY 3-36 levels.

[Time Frame: Changes in concentration (area under the curve AUC) from 30 minutes prior to breakfast to 180 minutes after consumption of test breakfasts (Part II of the study)]

6. Difference of HbA1c levels in high egg consumers as compared to low egg consumers  
This will be measured by taking blood on the visit 1.

[Time Frame: Changes in blood concentration (arbitrary units AU) on visit 1 (Part II of the study)]

7. Difference in Homeostasis Model Assessment-Insulin resistance (HOMA-IR) compared between different test breakfasts

This will be calculated using blood glucose and insulin levels.

[Time Frame: Changes in HOMA-IR values (arbitrary units AU) on visit 1 and 2 after providing test breakfasts (Part II of the study)]

8. Difference in Resting Metabolic Rate (RMR) compared between different test breakfasts  
RMR will be assessed following different test breakfasts on visit 1 and 2.

[Time Frame: Changes in RMR (kcal/24hrs) on visit 1 and 2 following each test breakfast (Part II of the study)]

9. Difference in total energy intake (kcal) compared between Remote Food Photography Method (RFPM), 7-day food record and 24-hour recall

Comparison of mean energy intake as determined by RFPM with mean energy intake determined by 7-day food record and a single 24-hour recall.

[Time Frame: Day 1-7 of the ecological momentary assessment part (Part I) of the study]

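### Secondary outcome 6 lists egg intake and HbA1c as a high-versus-low consumer contrast, but the SAP analyses HbA1c only by regression on egg intake, so the listed endpoint has no planned analysis

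*Combined protocol and SAP*

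**What the plan says.** **Outcome list.** Secondary Outcome Measures, item 6, is "Difference of HbA1c levels in high egg consumers as compared to low egg consumers", from blood taken at visit 1. The item does not define high and low consumers. Hypothesis 2 and the SAP do: "individuals in the top quartile based on egg consumption" against "individuals in the bottom quartile based on egg consumption". The Food Frequency Questionnaire section says the FFQ places subjects in quartiles, and primary outcomes 2 and 4 identify high and low consumers by FFQ.

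**SAP.** The quartile comparison, by Welch or Wilcoxon test, is specified for "mean EI and saturated fat intake of the high egg consumers" against those of the low consumers. HbA1c is not mentioned there. It appears in the next paragraph as the fourth outcome of the regressions: "Linear regression models will be constructed to examined the associations between a) total EI, b) saturated fat intake and c) egg intake". No subset of subjects is named and no covariates are listed, but regression assumptions are to be checked.

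**Hypotheses.** Hypothesis 4, which follows a list of baseline outcomes that includes HbA1c, reads "Above outcome variables will not be associated with egg intake determined by RFPM". Hypothesis 3 adjusts the companion associations for age, sex, BMI and waist circumference.

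**The concern.** A reader who goes from outcome 6 to the SAP finds no analysis for it. A reader who starts from the SAP finds an egg-HbA1c analysis that answers Hypothesis 4 but matches no listed outcome. One question thus has two definitions, and only one has a method.

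This does not look like shorthand. Primary outcomes 2 and 4 use the same high-versus-low wording and each has a matching quartile test in the SAP. The proposal attached at the end of the document also uses quartiles for intake and association or correlation for HbA1c. Outcome 6 is the exception.

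Two things are at stake. Unless the definition is fixed beforehand, which result is reported for outcome 6 could be settled after the data are seen. And if the outcome is reported as listed, the middle half of the sample goes unused, on a question where the protocol predicts no association.

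**Working it through.** **1. The two definitions side by side**

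| | Outcome 6 as listed | SAP regression and Hypothesis 4 |
|---|---|---|
| Subjects | top and bottom quartiles: 48/4 = 12 each, 24 in all, 48 − 24 = 24 unused | no restriction stated, so read as all 48 |
| Estimand | difference in mean HbA1c | slope of HbA1c on egg intake |
| Exposure instrument | FFQ | RFPM (Hypothesis 4) |
| SAP method | none | linear regression |

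**2. The plan's own power figure.** The attached proposal states 80% power for a correlation of 0.43 with 40 subjects at a level of 0.05. With Fisher's z, two-sided: r = tanh[(1.960 + 0.842)/√(40 − 3)] = tanh(0.461) = 0.431. The figure reproduces. It describes a whole-sample correlation, not a quartile contrast. At 48 subjects the same formula gives tanh(2.802/√45) = 0.395.

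**3. Power of the two analyses at 48 subjects.** The documents give no HbA1c SD, target difference or expected correlation, so the true correlation r is an assumption shown over a range. Further assumptions: bivariate normal data, no ties, both analyses using the same error-free ranking of intake, two-sided 0.05, no adjustment for covariates or multiplicity. Simulated power:

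| True r | Regression, n = 48 | Welch, 12 vs 12 | Loss (points) |
|---|---|---|---|
| 0.10 | 10% | 9% | 1 |
| 0.20 | 28% | 22% | 6 |
| 0.30 | 56% | 44% | 12 |
| 0.39 | 80% | 67% | 13 |
| 0.40 | 82% | 70% | 12 |
| 0.45 | 91% | 81% | 10 |
| 0.50 | 96% | 89–90% | about 7 |

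For 80% power the regression needs r of about 0.39. The quartile test needs about 0.445, a group difference of about 1.20 SD.

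**4. Why half the subjects is not half the information.** The mean of the top quarter of a standard normal is φ(0.674)/0.25 = 1.271, so the expected group difference in HbA1c is 2 × 1.271 × r SD. At r = 0.40 that is 1.017 SD. The within-group SD is √(1 − 0.16 + 0.16 × 0.242) = 0.937, so the standardised difference is 1.017/0.937 = 1.085. Selecting the extremes enlarges the contrast and recovers much of what is dropped. By Fisher's z, a regression in 37 subjects has 69.5% power at r = 0.40, matching the 70% of the quartile test. The quartile test is therefore worth about 37 subjects, not 24.

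**5. Sensitivity.** With right-skewed intake (lognormal, log-SD 0.7, assumed), power at r = 0.40 is 76% vs 52%. If the FFQ ranks subjects imperfectly relative to RFPM intake (assumed squared correlation 0.8 down to 0.5), quartile power at r = 0.40 falls to 59% down to 40%. The documents support no particular value for either assumption.

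**The case against.** The strongest reply is that the more powerful analysis is already the one the SAP specifies. Hypothesis 4 and the attached proposal also treat eggs and HbA1c as an association, and no section commits to a 12-versus-12 test of HbA1c. On this view, one label in the outcome list was not harmonised with the SAP. That is largely right, and it limits the severity. The mismatch remains: a listed outcome should be reportable as listed, and this one has no method.

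The second reply is that the loss is small at both ends of the range. It is about 1 point at r = 0.10, where neither analysis has useful power, and about 7 at r = 0.50, where both do well. This stands, and the table shows it.

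The third concerns the exposure model. The FFQ has five frequency boxes and three egg-count boxes, so ties may prevent groups of exactly 12, and normal continuous intake is a simplification. This stands too. The figures indicate size and are not predictions.

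A reader might infer that outcome 6 tilts the study toward its predicted null. The documents do not support that. Lower power is not bias, nothing shows an intention to report the weaker result, and an unadjusted contrast could be confounded in either direction.

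**Conclusion.** The mismatch is in the text. Outcome 6 and the SAP analysis of HbA1c differ in subjects, estimand and exposure instrument, and the outcome as listed has no planned analysis. Two readings are inferences: that high and low mean quartiles (from Hypothesis 2 and the SAP) and that the regression uses all subjects (no restriction is stated).

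Reporting the outcome as listed would cost about 6 to 13 points of power for true correlations from 0.20 to 0.50, and almost nothing at 0.10, under the normal, untied assumptions above.

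It would go too far to say that half the information is lost, or that the regression would establish the absence of an association. A non-significant result under either analysis does not show that, and the plan gives no equivalence bound. This is a cheap improvement of minor severity, confined to one secondary outcome.

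**What to change.** Redefine secondary outcome 6 as the slope, with 95% CI, of visit 1 HbA1c on RFPM-determined egg intake in all subjects, estimated by the linear regression already in the SAP. In that SAP paragraph, name RFPM as the source of egg intake, state that all subjects are included, and list the covariates the protocol gives for Hypothesis 3: age, sex, BMI and waist circumference. Changing the outcome line alone would leave the exposure instrument and the adjustment open. Keep mean HbA1c by FFQ quartile as a descriptive display without a test.

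The cost is a short edit to the outcome list and to one SAP paragraph, with no new data. The downside is that a slope is slightly harder to present than two group means and assumes linearity, which the SAP's planned check of regression assumptions should cover.
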